# Figure 2. Probabilities of further enrollment at the current dose, given varying true infection probabilities, numbers of subjects enrolled at the current dose, and decision thresholds

For illustration, with n=10 subjects enrolled in Cohort 1A at  $10^4$  TCID50, the probability of achieving 8 infections (solid line, top left panel) would be only 0.01 if the true infection probability were 0.4, compared to 0.67 if the true infection probability were 0.8.

Depending on the number of infections observed at each dose level, the final sample size for each dose group will be approximately 10, 15, 20 or 30. Figure 3 shows the estimated infection probabilities and associated exact 95% confidence intervals that would result from observing varying numbers of symptomatic influenza events at a given dose level. The maximum CI width occurs at 50% observed events. With 30 subjects enrolled at the optimal dose, this would correspond to observing 15 symptomatic influenza events and an estimated CI of (31.3%, 68.7%).

## Figure 3. Estimated symptomatic influenza probabilities and associated exact 95% CIs, given varying numbers of symptomatic influenza events observed and varying sample sizes

Table 3 gives the probability of observing one or more safety events, such as a solicited symptom or an SAE of a particular classification in varying total dose group sizes, given underlying true event probabilities.

Table 3. Probability (%) of observing at least one safety event, given varying underlying
event probabilities and dose group sizes

		Dose group Size		
True Event Probability	N=10	N=15	N=20	N=30
0.01 (Rare)	0.1	0.15	0.2	0.3
0.1 (Uncommon)	0.996	1.49	1.98	2.96
1 (Common)	9.56	14	18.2	26
10 (Very Common)	65.1	79.4	87.8	95.8

## 9.4 **Populations for Analyses**

- The Safety (SA) population will include all subjects who received study influenza challenge.
- The Intent-to-Treat (ITT) population will consist of all subjects who received study influenza challenge.
- The Per-Protocol (PP) population will include subjects in the ITT population with the following exclusions of data:
  - All data from any subjects who withdraw prior to the end of the challenge period
  - Data from any visit that occurs substantially out of window

- Data from all visits subsequent to major protocol deviations that could impact the validity of later data, such as:
  - Receipt of immunosuppression or any medications that may be associated with impaired responsiveness
  - Receipt of any investigational drug/investigational vaccine/licensed vaccine
  - Receipt of blood or blood products, or blood donation

Certain analyses may be done on subsets of these populations, such as infected subjects, or those receiving what is determined to be the optimal dose.

## 9.5 Statistical Analyses

Clinical (symptom and infection) and safety data through the last follow-up at Day 57 will comprise the primary clinical database for this study. Once the last subject has completed the final visit, the primary clinical database will be cleaned, monitored, and locked. The clinical study report (CSR), comprised of the final analyses of safety, clinical, and available immunological data will be completed by the Statistical and Data Management Coordinating Center (SDMCC) after the primary clinical database is locked and the separate statistical analysis plan (SAP) has been finalized. The CSR will be completed when all primary and secondary safety, clinical, and immunological endpoint data are available. Any available data from the exploratory endpoints may also be included. Additional exploratory endpoint data not available at the time of CSR preparation may be included in one or more addenda to the CSR.

Some analyses may be conducted on an expedited basis prior to the completion of the study and included in a "topline" report, to aid in decision-making regarding future studies. These analyses would not affect the conduct of this trial; subjects would be described by group but subject-level unblinding will not occur until the clinical database is locked. The topline results would be considered final and included in the CSR as well.

The formal SAP will elaborate on the analyses described here and will define which analyses would be included in an expedited report.

#### 9.5.1 General Approach

For descriptive analyses, continuous variables will be summarized by the non-missing sample size, mean, standard deviation, and the minimum, median, and maximum. Categorical variables will be summarized by frequencies and percentages of observed levels, based on the non-missing sample size. Titers will be summarized with geometric means, first across replicates to compute one value for each individual sample and then applied again across subjects within the same group.

Generally, summaries will be presented by challenge dose group, with sham placebo subjects pooled across all challenge cohorts into one group. For safety endpoints, summaries will include a column for all subjects receiving active challenge virus as well. Other groupings used for some analyses may include symptomatic/asymptomatic, shedding virus yes/no (i.e., RT-PCR+/RT-PCR-), and symptomatic influenza+/symptomatic influenza- or MMID+/MMID-.

Data listings will be presented sorted by clinical site or other grouping variable, subject, and then by visit number within subject, where applicable. All tables will be annotated with the total

population size relevant to that table, including any missing observations. The analysis population for each exhibit will be clearly indicated.

While the study was not designed for any formal group comparisons, hypothesis testing will be done for some endpoints and will be considered exploratory. For hypothesis testing related to safety endpoints, two-sided tests at the  $\alpha$ =0.05-level will be made without adjusting for multiple testing. For hypothesis testing of clinical endpoints, initially a global, two-sided test will be used to determine if there are differences between any groups. If the global test is significant at the  $\alpha$ =0.05-level, the Bonferroni-Holm stepdown procedure [9] will be used to control the type-I error across pairwise two-sided tests, but no adjustment will be made across endpoints; a familywise 5% error rate will be used to determine significance. For immunological, genomic, or physiological analyses involving hypothesis testing, more stringent thresholds for significance may be used, depending on the number of hypothesis tests comprising a related set of analyses.

For hypothesis tests of continuous endpoints, ANOVA will be preferred for tests across multiple groups and t-tests for pairwise tests. If histograms of the analysis data do not appear approximately normal even after log- or other transformation and the sample sizes for comparisons groups are too small for the application of the central limit theorem (which states that in sufficiently large samples, the sample mean is approximately normal), Wilcoxon rank-sum tests or other nonparametric methods may be utilized instead. For tests of categorical endpoints, exact binomial tests or Fisher's exact tests will be used.

Exact Clopper-Pearson confidence intervals will be computed for binary variables, where applicable, and for continuous variables confidence intervals will be computed based on the t-distribution with n-1 degrees of freedom, where n denotes the number of observations.

If other analysis approaches than those listed here are used, they will be clearly stated and justified in the SAP and/or CSR.

#### 9.5.2 Analysis of the Primary Endpoints

The three primary objectives for this study involve characterizing the infectivity and the symptom profile elicited by increasing doses of the study challenge virus, as well as determining the optimal dose for use in future challenge and vaccine studies.

The primary endpoints are:

- The percentage of subjects within a challenge dose group with detectable shedding by qualitative RT-PCR and symptom scores that meet the clinical case definition for symptomatic infection by the Modified Jackson Instrument score
- The percentage of subjects within each challenge dose group with detected viral shedding, the magnitude of viral shedding from Day 2 through Day 8, and the duration of viral shedding
- The computed symptom score from the modified Jackson symptom score, and the percentage of subjects with total symptom scores meeting criteria for symptomatic or asymptomatic categories

The probability of symptomatic influenza will be estimated for each challenge dose group, along with associated 95% exact confidence intervals. The optimal infectious dose will be the challenge dose group with the greatest estimated probability of symptomatic influenza which is

safe, as determined by the study halting criteria. If doses with similarly high observed AR have substantially different group sizes (e.g., 10 vs. 30), the lower limit of the estimated 95% CIs for the AR may be considered as well.

Viral shedding will be summarized by the number and percentage of subjects in each challenge dose group with positive qualitative and/or quantitative RT-PCR each day from Day 2 through the end of the challenge period (Day 8 or later, in the case of a subject not meeting discharge criteria on Day 8) excluding safety results reported after receipt of antiviral therapy. The probability of viral shedding at any point during the challenge (i.e., incidence) will be estimated along with the associated exact 95% CI, separately by challenge dose group. Peak viral shedding will be calculated for each subject as the maximum shedding from Day 2 through Day 8 or discharge, and total viral shedding will be calculated via the area under the curve (AUC) with study day on the x-axis and shedding on the y-axis. These will be calculated separately for quantitative RT-PCR and quantitative culture. Mean peak and total shedding based on the AUC will be calculated for each group along with 95% CIs, and comparisons will be made as described for continuous variables in Section 9.5.1. A Wilcoxon signed-rank test will be used to compare distributions of these variables between quantitative RT-PCR and quantitative culture across all subjects, to assess if these methods of viral quantification are consistent. Scatterplots will also be presented, along with Spearman rank-order correlation estimates. Duration of viral shedding will be calculated for each subject as the number of days (including non-consecutive) determined by qualitative or quantitative RT-PCR to be positive from Day 2 until discharge; means and 95% CIs will be calculated for each group and comparisons will be made.

Solicited influenza symptoms will be presented by the frequency and percentage of subjects reporting each symptom, severity, day, and challenge dose group. The self-reported (FLU-PRO) and investigator-assessed symptoms will be tabulated separately. Total symptom scores will be computed for each subject and each scoring algorithm. Mean scores for both algorithms will be calculated for each group, along with 95% CI, and the groups will be compared as described in Section 9.5.1. Additionally, the number and percentage of subjects meeting each scale's definition of symptomatic and asymptomatic will be cross-tabulated by challenge dose group. A Wilcoxon rank-sum test will be used to compare the distributions of each set of scores, across all subjects that received active challenge, to determine the agreement between the two symptom reporting methods.

Clinical endpoints (including the primary endpoints) will be assessed in the ITT population. Subjects who withdraw during the challenge period prior to meeting discharge criteria will be included in summaries where data are available. Subjects who withdraw during the challenge period and have yet to meet the relevant clinical case definition will be excluded from analyses of aggregate endpoints such as the incidence of symptomatic influenza.

If at least 10% of the analysis data would be dropped according to PP population exclusions described in Section 9.4, the PP population will be used as a sensitivity analysis for the primary ITT analysis.

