3.2.2. Viral Shedding Status and Duration of Viral Shedding

Viral shedding status will be determined for each participant on each study day during the challenge period, classified as follows:

- **RT-PCR+** if a qualitative RT-PCR result from the Biofire or Luminex multiplex assay is reported to be positive for Influenza A or Influenza A H3, and/or if a quantitative RT-PCR is reported to have detectable H3N2 virus.
- **RT-PCR-** if the qualitative RT-PCR results for Influenza A and Influenza A H3 are negative and the quantitative RT-PCR result indicates undetectable quantities of virus.

Detectable virus for the quantitative RT-PCR assay will be defined as being any quantity above a lower limit of detection (LLOD) reported by the laboratory conducting the assay.

Duration of viral shedding will be defined as time from the initial positive NP swab until the day after the final positive NP swab, with positivity defined as above. Intermittent negative results will be ignored for this computation.

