3.2.5. Symptom Scores

The cumulative Modified Jackson Score (MJS; see [Figure 4](#)) will be calculated as described in [Section 3.2.1](#).

The area under the MJS curve will be calculated for each participant from Day 2 through Day 8, for uninfected participants (see [Section 3.2.3](#)), or from the first RT-PCR+ day through the last, for infected participants; this calculation will be made as described above in [Section 3.2.4](#) for total viral shedding, except in this case scaled by the number of days over which symptoms are summed.

The FLU-PRO total severity score is defined as the mean score across all 32 items (see [Figure 5](#)), with component scores ranging from 0 to 4. Six domain scores are also computed as mean scores, representing symptom severity in each body system. Scores will be computed for each study day utilizing the maximum severity score per symptom, and cumulative FLU-PRO scores (for the total FLU-PRO score and component scores) will be computed as the sum of the daily scores over the relevant time period.

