5. GENERAL STATISTICAL CONSIDERATIONS

5.1. General Principles

The challenge period is defined as the day of study challenge (Day 1) through discharge from the confinement period (Day 8 or later).

Continuous variables will generally be summarized using the following descriptive statistics: non-missing sample size (denoted by “n”), mean or geometric mean, standard deviation, minimum, median, and maximum. Titers will be summarized with geometric means, first across replicates to compute one value for each individual sample and then across participants within clinical outcome groups. The frequencies and percentages (based on the non-missing sample size) of observed levels will be reported for categorical measures. Data listings will typically be sorted by site or other grouping variable (e.g. infection status), participant, and by visit number within participant, where appropriate. All tables will be annotated with the total population size relevant to that table, including any missing observations.

For continuous variables, confidence intervals will be computed based on the t-distribution, unless the data appear especially non-normal and the sample sizes for the analysis are insufficient to apply the central limit theorem. Bootstrap confidence intervals may be calculated instead if the t-distribution is determined to be unsuitable. For binary variables, confidence intervals will be computed using the exact Clopper-Pearson method.

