7.1.3. Viral Shedding – Timing, Duration, and Magnitude

Viral shedding is measured by qualitative and quantitative RT-PCR, which are both incorporated into determining viral shedding status (binary yes/no) for a given day, as described in [Section 3.2.2](#).

Qualitative RT-PCR status will be cross-tabulated with RT-qPCR status (RT-PCR+/undetectable) by challenge dose group in [Table 28](#). Qualitative RT-PCR results will be summarized for all targets of the multiplex assays for each study day during the challenge period in [Table 29](#) through [Table 32](#). An overall comparison of qualitative and quantitative RT-PCR results will be presented in [Table 33](#), to assess the agreement of the two assays.

The number of days to first detected viral shedding will be summarized by challenge dose group in [Table 34](#). The median number of days to infection and corresponding 95% CI will be estimated for each group via the Kaplan-Meier method, in order to account for the censoring of participants who never tested RT-PCR+ throughout the challenge period.

The number of total days with RT-PCR+ results will be summarized by challenge dose group in [Table 35](#). A summary of peak viral shedding, total viral shedding (via AUC), and the duration of viral shedding (from first positive through last positive) will be presented in [Table 36](#).

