Day 6	RT-qPCR+	x (x.x)	x (x.x)	x (x.x)	x (x.x)	x (x.x)	x (x.x)	x (x.x)	x (x.x)
	Undetectable Virus	x (x.x)	x (x.x)	x (x.x)	x (x.x)	x (x.x)	x (x.x)	x (x.x)	x (x.x)
Day 7	RT-qPCR+	x (x.x)	x (x.x)	x (x.x)	x (x.x)	x (x.x)	x (x.x)	x (x.x)	x (x.x)
	Undetectable Virus	x (x.x)	x (x.x)	x (x.x)	x (x.x)	x (x.x)	x (x.x)	x (x.x)	x (x.x)
Day 8+	RT-qPCR+	x (x.x)	x (x.x)	x (x.x)	x (x.x)	x (x.x)	x (x.x)	x (x.x)	x (x.x)
	Undetectable Virus	x (x.x)	x (x.x)	x (x.x)	x (x.x)	x (x.x)	x (x.x)	x (x.x)	x (x.x)
Anytime Post-Challenge ^a	RT-qPCR+	x (x.x)	x (x.x)	x (x.x)	x (x.x)	x (x.x)	x (x.x)	x (x.x)	x (x.x)
	Undetectable Virus	x (x.x)	x (x.x)	x (x.x)	x (x.x)	x (x.x)	x (x.x)	x (x.x)	x (x.x)

Note: N = Number of participants in the Safety population with available results.

^a The number of participants with viral shedding reported at any time point within the challenge period (Days 2 to 8+).

Table 29: Multiplex Respiratory Virus Assay Results by Virus, Subtype, and Study Day, 10⁴ TCID₅₀ Challenge Virus Group, Safety Population

Virus	Subtype ^a	Day 2 (N=X)		Day 3 (N=X)		Day 4 (N=X)		Day 5 (N=X)		Day 6 (N=X)		Day 7 (N=X)		Day 8 (N=X)		Days 9+ (N=X)		Anytime Post-Challenge (N=X)	
		n	%	n	%	n	%	n	%	n	%	n	%	n	%	n	%	n	%
Influenza	Any Subtype	X	X.X	X	X.X	X	X.X												
	Influenza A ^a	X	X.X	X	X.X	X	X.X												
	Influenza A 2009 H1N1	X	X.X	X	X.X	X	X.X												
	Influenza A H1	X	X.X	X	X.X	X	X.X												
	Influenza A H3 ^a	X	X.X	X	X.X	X	X.X												
	Influenza B	X	X.X	X	X.X	X	X.X												
Other	Any Subtype	X	X.X	X	X.X	X	X.X												
	Adenovirus	X	X.X	X	X.X	X	X.X												
	Bocavirus	X	X.X	X	X.X	X	X.X												
	Bordetella Pertussis	X	X.X	X	X.X	X	X.X												
	Coronavirus 229E	X	X.X	X	X.X	X	X.X												
	Coronavirus HKU1	X	X.X	X	X.X	X	X.X												
	Coronavirus NL63	X	X.X	X	X.X	X	X.X												
	Coronavirus OC43	X	X.X	X	X.X	X	X.X												
	Human Metapneumovirus	X	X.X	X	X.X	X	X.X												
	Mycoplasma Pneumoniae	X	X.X	X	X.X	X	X.X												
	Parainfluenza Virus 1	X	X.X	X	X.X	X	X.X												
	Parainfluenza Virus 2	X	X.X	X	X.X	X	X.X												
	Parainfluenza Virus 3	X	X.X	X	X.X	X	X.X												
	Parainfluenza Virus 4	X	X.X	X	X.X	X	X.X												
	Respiratory Syncytial Virus (unspecified)	X	X.X	X	X.X	X	X.X												
	Rhinovirus/Enterovirus	X	X.X	X	X.X	X	X.X												

Virus	Subtype ^a	Day 2 (N=X)		Day 3 (N=X)		Day 4 (N=X)		Day 5 (N=X)		Day 6 (N=X)		Day 7 (N=X)		Day 8 (N=X)		Days 9+ (N=X)		Anytime Post- Challenge (N=X)	

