2	x	x.x	x	x.x	x	x.x	x	x.x
3-6	x	x.x	x	x.x	x	x.x	x	x.x
7+	x	x.x	x	x.x	x	x.x	x	x.x

Notes: N = Number of participants in the Safety population; n = Number of participants reporting a given number of days of positive qualitative and/or quantitative RT-PCR results.

Table 36: Summary of Peak, Total, and Duration of Viral Shedding by Challenge Dose Group, Safety Population*

Variable	Statistic	10 ⁴ TCID ₅₀ Challenge Virus (N=X)	10 ⁵ TCID ₅₀ Challenge Virus (N=X)	10 ⁶ TCID ₅₀ Challenge Virus (N=X)	Sham Inoculum (N=X)
Peak viral load (log-10 copies/mL)	Mean (95% CI)	x.x (x.x, x.x)	x.x (x.x, x.x)	x.x (x.x, x.x)	x.x (x.x, x.x)
	Standard Deviation	x.x	x.x	x.x	x.x
	Minimum	x.x	x.x	x.x	x.x
	Median	x.x	x.x	x.x	x.x
	Maximum	x.x	x.x	x.x	x.x
AUC (log-10 copies/mL) ^a	Mean (95% CI)	x.x (x.x, x.x)	x.x (x.x, x.x)	x.x (x.x, x.x)	x.x (x.x, x.x)
	Standard Deviation	x.x	x.x	x.x	x.x
	Minimum	x.x	x.x	x.x	x.x
	Median	x.x	x.x	x.x	x.x
	Maximum	x.x	x.x	x.x	x.x
Duration of Viral Shedding ^b	Mean (95% CI)	x.x (x.x, x.x)	x.x (x.x, x.x)	x.x (x.x, x.x)	x.x (x.x, x.x)
	Standard Deviation	x.x	x.x	x.x	x.x
	Minimum	x.x	x.x	x.x	x.x
	Median	x.x	x.x	x.x	x.x
	Maximum	x.x	x.x	x.x	x.x

Note: N = Number of participants in the Safety population followed for the entire challenge period.

^aArea under the curve calculated using raw viral copies/mL through discharge from the challenge unit, then log-10 transformed.

^bDuration measured as the number of days between the first positive and last negative RT-PCR results, inclusive, regardless of any intermittent negative results.

Table 37: Maximum Severity of Participant-Reported FLU-PRO Symptoms by Study Day, 10⁴ TCID₅₀ Challenge Virus Group, Currently Infected Participants in the Safety Population

		Baseline (N=XX)		Day 1 (Post-Challenge) (N=XX)		Day 2: RT-PCR+ (N=XX)		Day 3: RT-PCR+ (N=XX)		Day 4: RT-PCR+ (N=XX)		Day 5: RT-PCR+ (N=XX)		Day 6: RT-PCR+ (N=XX)		Day 7: RT-PCR+ (N=XX)		Day 8: RT-PCR+ (N=XX)		Days 9+: RT-PCR+ (N=XX)		Anytime Post-Challenge ^a : RT-PCR+	
Symptom	Extent	n	%	n	%	n	%	n	%	n	%	n	%	n	%	n	%	n	%	n	%	n	%
Any Symptom	0	x	x.x	x	x.x	x	x.x	x	x.x	x	x.x	x	x.x	x	x.x	x	x.x	x	x.x	x	x.x	x	x.x
	1	x	x.x	x	x.x	x	x.x	x	x.x	x	x.x	x	x.x	x	x.x	x	x.x	x	x.x	x	x.x	x	x.x
	2	x	x.x	x	x.x	x	x.x	x	x.x	x	x.x	x	x.x	x	x.x	x	x.x	x	x.x	x	x.x	x	x.x
	3	x	x.x	x	x.x	x	x.x	x	x.x	x	x.x	x	x.x	x	x.x	x	x.x	x	x.x	x	x.x	x	x.x
	4	x	x.x	x	x.x	x	x.x	x	x.x	x	x.x	x	x.x	x	x.x	x	x.x	x	x.x	x	x.x	x	x.x
Nose																							

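### The SAP drops, without declaring it, the protocol's exclusion of post-antiviral safety results from the daily shedding summary, and shedding duration runs through on-treatment days with nothing to mark them

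*Protocol*

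**What the plan says.** **Protocol.** Section 9.5.2 summarises qualitative and quantitative RT-PCR positivity for each day from Day 2 to the end of the challenge period, "excluding safety results reported after receipt of antiviral therapy". The clause belongs to that sentence alone. Later in the same paragraph, duration is a count of days "determined by qualitative or quantitative RT-PCR to be positive from Day 2 until discharge", with no antiviral cut; peak and AUC have none either.

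**When antivirals start.** Footnote 8 to the Schedule of Activities and Section 4.1 allow treatment from Study Day 6. Section 4.1 adds that it follows receipt of the test results and is offered to subjects who are still symptomatic or RT-PCR positive that day. Section 6.5.1 offers an antiviral to anyone without two consecutive negative days by Day 8.

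**SAP.** Section 3.2.2 classes a day as positive on either assay and adds: "Duration of viral shedding will be defined as time from the initial positive NP swab until the day after the final positive NP swab". Section 5.1 runs the challenge period to discharge. Section 7.1.3 says: "The number of total days with RT-PCR+ results will be summarized by challenge dose group". Tables 28 to 32 include rows or columns for Day 8 onward or Day 9 onward. AUC in Table 36 is "calculated using raw viral copies/mL through discharge from the challenge unit, then log-10 transformed". The area under the Modified Jackson Score (MJS) curve runs from Day 2 through Day 8 for uninfected participants, "or from the first RT-PCR+ day through the last, for infected participants". None of these places mentions antivirals. The per-protocol exclusions in 5.3.3 do not name them, and the post-antiviral rule in 4.6.2 concerns adverse-event classification only. Section 14 states that no substantive change was made to the protocol's analysis.

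**The concern.** There are two linked problems.

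First, a protocol analysis rule is missing from the SAP and its removal is not declared. Protocol 9.5.1 requires departures to be stated and justified in the SAP or study report. The SAP did so for another change, the addition of quantitative RT-PCR to the case definition in 3.2.1.

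Second, treatment depends on the outcome being measured. A subject still positive on Day 6 is eligible for a drug given to end the infection, and that subject's later swabs then define when shedding ended. If the antiviral works, observed duration is cut in persistent shedders only, and more often in a dose group that has more of them. Duration is listed under primary objective 2 and reported by dose group with confidence intervals. Tables 28 and 36 are marked for the topline report, whose results SAP 5.2 treats as final. A reader of those tables could not tell which days were on treatment.

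**Working it through.** The plan states no figure on this point, so there is none to reproduce. The check compares the rules and then counts exposure.

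**1. Rules side by side**

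| Output | Protocol 9.5.2 | SAP |
|---|---|---|
| Daily positivity | Post-antiviral safety results excluded | No exclusion (3.2.2, 5.1, Tables 28 to 32) |
| Total positive days | No antiviral rule | No antiviral rule (Table 35) |
| Duration | To discharge, no antiviral rule | First to last positive, no antiviral rule (3.2.2, Table 36) |
| AUC | No antiviral rule | To discharge, no antiviral rule (Table 36) |

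The undeclared departure is in the first row. The others are gaps common to both documents.

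**2. Duration days after treatment start**

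By SAP 3.2.2, duration = last positive day − first positive day + 1. For a Day 6 start, the Day 6 swab precedes treatment because treatment waits for its result. Days after start = last positive day − 6.

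- Last positive Day 8, first positive Day 2: (8 − 6)/(8 − 2 + 1) = 2/7. First positive Day 4: 2/5.
- Last positive Day 10, the planned end of confinement in protocol 4.1: first positive Day 2, 4/9; first positive Day 4, 4/7.

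These are days on which a subject stayed positive despite treatment. The possible bias lies in days lost by subjects who cleared because of treatment, and those days are not observed. Table 36 footnote b words the end of duration differently; the counts follow 3.2.2.

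**3. What a bias could look like (assumed inputs)**

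Shift in mean duration = share treated × days shortened. The documents give neither input. Taking 20% to 60% treated and 1 to 3 days shortened, the shift runs from 0.2 × 1 = 0.2 to 0.6 × 3 = 1.8 days. If two dose groups had 20% and 60% treated and lost 2 days each, their means would shift by 0.4 and 1.2 days, an artificial difference of 0.8. A range this wide shows that the size is unknown.

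**4. AUC**

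Assumptions: linear trapezoid over Days 2 to 8, peak 10^7 copies/mL, rise of 1 or 2 log10 per day, fall of 0.5 or 1 log10 per day, and full clearance to 50 copies/mL on Days 7 and 8. The drop in log10 AUC is 0.000–0.003 for a peak on Day 3, 0.000–0.011 on Day 4, 0.004–0.036 on Day 5 and 0.039–0.134 on Day 6. The largest case (peak Day 6, rise 2, fall 0.5) has area 13.763 × 10^6 without clearance and 10.101 × 10^6 with it; log10(13.763/10.101) = 0.134. Raw copies near the peak dominate the area, so late days hardly count.

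**5. Attack rate**

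A subject positive on Day 6 needs only one other positive day. Full symptom days after a Day 6 start number 0, 1 and 2 of 5 in the windows Days 2–6, 3–7 and 4–8, so the score can be reached wholly before treatment. The main remaining exposure is a subject first positive on Day 6.

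**The case against.** The strongest reply is that inclusion is the stated rule for duration. Both documents run it to the last positive or to discharge, which describes shedding under protocol-specified care, applied alike to every dose group. A pre-treatment duration answers a different question. This stands: keeping on-treatment days is a legitimate choice. It does not excuse leaving those days unmarked, since treatment is triggered by persistent positivity and its frequency may differ by dose. Table 79 and Listing 17 will show antiviral use, but not linked to the shedding days.

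The protocol clause is also narrow and vague. Safety results is undefined. Protocol 8.2 lists the local multiplex assay among the clinical laboratory evaluations, so the clause may not reach research quantitative RT-PCR. A reader might infer that the protocol excluded every post-antiviral result; the wording does not support that. But even on the narrow reading the SAP omits the rule, because 3.2.2 counts those qualitative positives. Whether the omission is substantive in the sense of SAP 14 is a judgement.

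Outright restoration has a cost too. Dropping treated subjects' later results removes persistent shedders from the Day 7 and later percentages, so the excluded version is selective in its own way.

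Finally, little rests on this. Under protocol 9.5.2 the optimal dose is chosen on attack rate and safety. The per-day MJS AUC sits among exploratory outputs, and because it is scaled per day the direction of any effect is unclear. This stands, and it confines the point to descriptive shedding results.

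**Conclusion.** The point holds in a limited form. Following the SAP as written departs from a protocol rule for daily shedding without saying so. It also reports a duration that may be truncated by treatment in persistent shedders. The textual part needs no assumption. The truncation part assumes that antivirals given from Day 6 shorten RT-PCR positivity; its size cannot be derived, because the documents give neither the number treated nor an effect.

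Three stronger readings are not supported:

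- That the attack rate or the choice of dose is compromised. The case definition can be met by Day 6, before treatment starts.
- That 2/7 or 4/9 measures the bias. Those fractions count exposed days only.
- That antivirals given at early withdrawal add on-treatment days to Table 36. The Schedule of Activities has no nasopharyngeal swab at early termination, and Table 36 counts only participants followed for the whole challenge period.

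The differing Day 6 treatment triggers in footnote 8 and Section 4.1 are a matter of conduct, relevant only if a cohort remains to be challenged.

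**What to change.** In the SAP, before the topline tables are final:

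1. Derive for each study day a flag for before or after the first antiviral dose, using recorded medication start days (Listing 17). Report the number treated and the start day by dose group beside Tables 28, 35 and 36.
2. Present the daily shedding summary with and without post-antiviral results. State which assay the protocol's term safety results covers, and list any departure from protocol 9.5.2 in Section 14. Note beside the table that exclusion removes persistent shedders from the percentages for Day 7 onward.
3. Add one sensitivity analysis of duration that uses only days up to antiviral start. Show treated subjects still positive at start as lower bounds, and label the censoring informative, since treatment depends on still shedding or having symptoms.

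Cutting every subject at Day 6 is not a good substitute. For anyone positive on Day 6 it gives 6 − first positive day + 1 = 7 − first positive day, which measures onset and not duration.

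The cost is one derived flag, one extra table and some SAP text, with no new data. The downside is that pre-treatment duration is only a lower bound in treated subjects.
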